**Table 4-2: Objectives and Endpoints for Part 2.**

Objectives	Endpoints
Primary	

To evaluate the association between baseline tissue TMB/bTMB and clinical efficacy (ORR) for participants in Part 2

	

The clinical efficacy will be measured by the analysis endpoint of objective response rate (ORR). The association of ORR with baseline tissue TMB and bTMB will be assessed

Secondary	

To investigate bacterially generated and human components enteric biomarkers and identify potential associations with clinical outcomes, including safety and efficacy for participants

	

ORR, PFS, OS

Incidence of AES, SAEs, and select AEs

- Objective response rate (ORR):** The proportion of patients with best overall response (BOR) of RECIST 1.1 defined confirmed complete response (CR) or partial response (PR) in a pre-defined study population.
- Disease control rate (DCR):** The proportion of patients with best overall response (BOR) of RECIST 1.1 defined complete response (CR), partial response (PR), or stable disease (SD) in a pre-defined study population
- Duration of response (DOR):** DOR is defined as the time between the date of the first confirmed response (CR/PR) to the date of the first documented tumor progression (per RECIST 1.1) or death due to any cause. Participants who neither progress nor die will be censored on the date of their last evaluable tumor assessment. Participants who started any subsequent anti-cancer therapy without a prior reported progression will be censored at the last evaluable tumor assessment prior to or on the date of initiation of subsequent anti-cancer therapy.

- **Time to response (TTR):** TTR is measured from the time of first dosing date to the time the criteria for CR/PR are first met.
- **Progression free survival (PFS):** PFS is defined as the time from first dosing date to the date of the first documented tumor progression (per RECIST) or death due to any causes. Participants who neither progress nor die will be censored on the date of their last evaluable tumor assessment. Participants who started any subsequent anti-cancer therapy without a prior reported progression will be censored at the last evaluable tumor assessment prior to or on the date of initiation of subsequent anti-cancer therapy.

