- **Overall survival (OS):** OS is defined as the time from first dosing date to the date of death. If a participant didn't die, OS will be censored on the last date the participant was known to be alive.

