**Table 9.6-1: Biomarker Assessment Schedule for Part 1**

[figure not shown]
Study Day	
Screening	
Cycle 1 Day1 (Week 1)	
Cycle 1 Day 29 (Week 5)	
Cycle 2 Day 15 (Week 9)	
Cycle 3 Day 1 (Week 13)	
Progression	

[figure not shown]
**Part 2** biomarker samples (blood and tumor tissue) for TMB analyses will be collected at screening. Fresh biopsy tissue is preferred for enrollment; follow lab manual for details. Archival tissue samples that are less than 3 months old may be submitted. For archival tissue, FFPE tissue block (preferred) or submission of 15 unstained tumor tissue sections for PDL-1 and TMB testing will be required. [REDACTED]

[REDACTED]

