### 10.3 Statistical and Computational Analyses

The association between ORR and tumor mutational burden will be explored using logistic regression model among treated patients evaluable for tumor mutational burden.

Due to limited participants as compared with the number of biomarkers that will be evaluated for the second co-primary objective, a multiple logistic regression model, or penalized regression methods (Elastic Net, implemented in SAS procedure GLMSELECT) will be used to assess the potential association between candidate biomarkers in peripheral blood and tumor tissue at baseline and on-treatment with clinical efficacy measures. The primary endpoint will be ORR, and other clinical efficacy measures will be analyzed as part of the secondary endpoints.

The analysis of the primary endpoint ORR will take place after the last treated subject is followed for [REDACTED]. Additional survival analysis will be conducted with longer follow up.

The statistical analysis plan will be developed and finalized before database lock and will describe the selection of participants to be included in the analyses, and procedures for accounting for missing, unused, and spurious data. Below is a summary of planned statistical analyses of the primary and secondary endpoints.

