### 10.3.1 Efficacy Analyses

Endpoint	Analysis Methods
Primary:	
ORR	
In Part 1, logistic regression model and ROC analysis will be used to evaluate tumor mutational burden as a candidate biomarker of ORR of nivolumab and ipilimumab combination therapy.
 
Multiple logistic regression or penalized regression will be used to screen for (baseline and post baseline) biomarkers simultaneously
 
ORR will be calculated for sub-groups identified by logistic or penalized regression methods, and the confidence interval by Clopper-Pearson method will be provided
 
In Part 2, ROC analysis will be used to confirm cutoffs for baseline tissue TMB and blood TMB that identify subjects who will experience therapeutic benefit based on ORR. Logistic regression will be conducted.
 
ORR will be calculated for TMB (tissue and blood) sub-groups and the confidence interval by Clopper-Pearson method will be provided.

Secondary	
DCR, DOR, TTR, PFS, and OS	
The analysis conducted for ORR will be repeated for other efficacy endpoints of interest. For PFS, OS and DOR, for selected patient sub-groups, Kaplan-Meier curves will be provided, and median of time to events and the associated confidence interval will be calculated.
 
Descriptive summary statistics of TTR will be provided for patients with a BOR of CR or PR.

Exploratory	

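### PFS and OS run from first dose, yet Section 10.3.1 carries post-baseline biomarkers into them with no landmark rule, while the Part 1 secondary objective is limited to baseline biomarkers

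*Combined protocol and SAP*

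**What the plan says.** - **Time origin.** In Section 4, below Table 4-2: "PFS is defined as the time from first dosing date to the date of the first documented tumor progression" (or death), and "OS is defined as the time from first dosing date to the date of death". DOR has another origin; its definition opens with "DOR is defined as the time between the date of the first confirmed response (CR/PR".
- **Screen.** Section 10.3.1, primary endpoint: "Multiple logistic regression or penalized regression will be used to screen for (baseline and post baseline) biomarkers simultaneously". Sub-groups then come from the fitted model. Section 10.1 gives the example of cutting a patient-level risk computed from the model covariates.
- **Extension to PFS and OS.** Section 10.3.1, secondary endpoints: "The analysis conducted for ORR will be repeated for other efficacy endpoints of interest", followed by "For PFS, OS and DOR, for selected patient sub-groups, Kaplan-Meier curves will be provided, and median of time to events" with confidence intervals. Section 10.3, directly after describing the analysis of baseline and on-treatment markers: "The primary endpoint will be ORR, and other clinical efficacy measures will be analyzed as part of the secondary endpoints".
- **Sampling times.** Table 9.6-1 lists screening, Weeks 1, 5 and 9, the row that begins "Cycle 3 Day 1 (Week 13", and progression. Section 9.6 places tumor biopsies at screening, Week 5 and progression.
- **Counterweight.** Table 4-1 words the Part 1 secondary objective, the one that carries PFS and OS, for sub-groups formed from baseline markers.

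The visible text contains no landmark, delayed entry or time-dependent covariate.

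**The concern.** A participant can be placed in a sub-group by a Week 9 or Week 13 result only after giving that sample. Anyone who died earlier cannot be in the group, yet the clock starts at first dose. The stretch before sampling then counts as survival that no member could have failed to reach, and the Kaplan-Meier median is lengthened. A model-based risk score has the same property: the latest marker in it sets the lead time. The resampling adjustment in Section 10.1 addresses selection bias in sub-group ORR and would not repair a time origin that is the same in every resample.

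At stake are the absolute medians. Set beside a baseline-defined sub-group, all treated participants or another trial, an on-treatment sub-group could look better simply because its members lived long enough to be sampled.

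**Working it through.** The plan states no PFS or OS figure for an on-treatment sub-group, so there is nothing of its own to reproduce. It also gives no planning value for PFS or OS. The inputs below come from the CA209012 tables in Section 3.2.2 and are assumptions for this check.

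**Inputs**
- Median PFS m: 3.9 months (cohort Q, same schedule) and 8.1 months (cohort P), Table 3.2.2-2.
- 1-year OS: 69% (cohort Q, Table 3.2.2-2). Range: 58% and 83%, the values for arms N and Q among PD-L1 expressers in Table 3.2.2-3.
- Sampling time L after first dose: Week 5 = 28 days = 0.92 months; Week 9 = 56 days = 1.84; Week 13 = 84 days = 2.76.

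**Closed form.** With a constant hazard, a group that must be event-free to L has a median from first dose of m + L instead of m.

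OS: m = 12 × ln 2 / (−ln 0.69) = 22.4 months.

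| 1-year OS | m | Week 5 | Week 9 | Week 13 |
|---|---|---|---|---|
| 69% | 22.4 | 23.3 (+4%) | 24.3 (+8%) | 25.2 (+12%) |
| 58% | 15.3 | 16.2 (+6%) | 17.1 (+12%) | 18.0 (+18%) |
| 83% | 44.6 | 45.6 (+2%) | 46.5 (+4%) | 47.4 (+6%) |

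PFS at Week 13, if nobody who has progressed is sampled: 3.9 + 2.76 = 6.7 months (+71%), or 8.1 + 2.76 = 10.9 (+34%). At Week 9 on the same terms: 5.7 (+47%) or 9.9 (+23%).

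**Fit of the model.** With m = 3.9 it puts 41% of events within 3 months; Section 3.2.2 reports 15/39 = 38% progressing by then in cohort Q. It fits less well at 24 weeks: 37% event-free against 47% reported. The figures are therefore orders of size.

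**Adding the scan schedule.** Under Section 9.1.1.1 and Table 9.1.1.1-1 the first mandatory scan is 8 weeks (± 1 week) after first dose; the Week 5 CT is optional. The Week 5 biopsy (± 1 week) falls at most 5 weeks after first dose, before the earliest scheduled scan at 7 weeks. A simulation of 1,000,000 patients used 8-weekly scans, 1-year OS of 69%, latent median time to progression from 2.6 to 8.0 months, and 0%, 25% or 50% of progressed patients still giving the sample:

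- Week 5: median PFS 3.7 against 3.7 months for everyone (7.4 against 7.0 in the slowest case). Only early deaths, about 3%, are removed.
- Week 13, no progressed patient sampled: 3.7 becomes 5.5, or 7.0 becomes 9.2.
- Week 13, half of progressed patients sampled: 3.7 becomes 3.7 to 5.5, or 7.0 becomes 7.4. Between 8% and 24% of the sub-group had then already had the PFS event before the marker was measured.

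These medians tend to fall on scan dates and so move in steps. The 12-month restricted mean is smoother: at Week 13 it rises by 1.5 to 1.9 months with no progressed patient sampled, and by about 0.9 months with half sampled.

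**Same-visit contrasts.** Marker-high and marker-low patients sampled at one visit have medians m1 + L and m2 + L. The difference m1 − m2 is unchanged and the ratio moves toward 1.

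**The case against.** The strongest reply is that the plan never commits to Kaplan-Meier medians for on-treatment sub-groups. It says only that sub-groups will be selected, and Table 4-1 speaks of baseline markers. That is fair: the problem is conditional, and the first request is to reconcile Table 4-1 with Sections 10.3 and 10.3.1. It does not dispose of the point, because those two sections carry the post-baseline screen to PFS and OS without the restriction.

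A reader might infer more than the documents support:

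- **That PFS time before sampling is event-free by construction.** It is not. Section 8.1.2 allows treatment after RECIST progression, so a sample can follow a PFS event. The complete biomarker data set in Section 10.2 also admits a participant whose only post-baseline biopsy was taken at progression, which pulls PFS the other way.
- **That Week 5 PFS medians rise by 24%.** The closed form gives 3.9 + 0.92 = 4.8 months, but it ignores that the first mandatory scan comes later.
- **That a false early marker would emerge.** Contrasts within one sampling visit share the lead time.

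It can also be said that the study is exploratory, that no formal test is planned, and that a SAP will follow. Exploratory status does not remove bias from an estimated median. Section 10.3 describes what the SAP will cover without mentioning time origin, though a SAP not in this text could contain a rule. What is collected at Weeks 9 and 13 is not visible in Table 9.6-1, so the size at those visits depends on content that cannot be seen.

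**Conclusion.** The point holds in a limited form, for Part 1 only; the visible Part 2 TMB analysis uses baseline markers. Sections 10.3 and 10.3.1 on one side and Table 4-1 on the other disagree about which markers may define PFS and OS sub-groups, and no time-origin rule covers the wider reading.

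If that reading is followed, the OS bias is certain in direction and modest in size: 4% to 12% at 69% 1-year OS, and 2% to 18% over the range tried. For PFS, 6.7 months in place of 3.9, or 10.9 in place of 8.1, is a Week 13 upper bound under a constant hazard with no progressed participant sampled. Sampling after progression shrinks the shift in the median, possibly to nil, but then mixes in participants whose event came before the marker. Week 9 lies between, and depends on whether the sample is taken before or after the first scan is acted on. Week 5 PFS is practically unaffected. DOR is outside this mechanism. All sizes rest on the CA209012 values.

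**What to change.** In Section 10.3.1 (and the SAP) choose one of two rules and align Table 4-1 with it:

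1. Limit PFS and OS sub-groups to baseline markers, as Table 4-1 already says; or
2. For any sub-group that uses an on-treatment sample, start the clock at a fixed landmark at the sampling visit, among participants still event-free for that endpoint (alive for OS; alive and progression-free for PFS), or enter the marker as a time-dependent covariate. Keep first dose as time zero for baseline markers.

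Under either rule, do not form PFS sub-groups from progression samples. Under the second, report how many participants were excluded by an earlier event.

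The cost is a sentence or two and a landmark flag; no new data are needed. The downside is that early-event participants leave the on-treatment curves and must be counted separately. Under the closed-form assumptions, of about 100 treated in Part 1, some 39 (m = 3.9) or 21 (m = 8.1) would have had a PFS event before the Week 13 landmark, and about 8 would have died at 69% 1-year OS.

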### 10.3.2 Safety Analyses

[figure not shown]
All safety analyses will be performed on all treated participants.

Endpoint	Analysis Methods
Primary Event rate	AEs, including death, SAE, and AEs defined by safety monitoring test, will be summarized for all treated participants, and by sub-groups when applicable.

#### **10.3.4    *Other Analyses***

The population pharmacokinetics analysis and pharmacodynamic analyses will be presented separately from the main clinical study report.

**12 APPENDICES**

**APPENDIX 1 ABBREVIATIONS AND TRADEMARKS**

Term	Definition
AE	adverse event
ACLS	advanced cardiac life support
AI	accumulation index
ALT	alanine aminotransferase
ANC	absolute neutrophil count
AST	aspartate aminotransferase
AT	aminotransaminases
AUC	area under the concentration-time curve
A-V	atrioventricular
$\beta$ -HCG	beta-human chorionic gonadotrophin
BID, bid	bis in die, twice daily
BLQ	below limit of quantification
BMI	body mass index
BMS	Bristol-Myers Squibb
BP	blood pressure
BUN	blood urea nitrogen
C	Celsius
Ca ++	calcium
Cavg	average concentration
CBC	complete blood count
Cexpected-tau	expected concentration in a dosing interval
CFR	Code of Federal Regulations
CI	confidence interval
Cl 	chloride
CLcr	creatinine clearance
cm	centimeter
Cmax, CMAX	maximum observed concentration
Cmin, CMIN	minimum observed concentration
CNS	Central nervous system

Term	Definition
CRC	Clinical Research Center
CRF	Case Report Form, paper or electronic
Ctrough	Trough observed plasma concentration
CV	coefficient of variation
CYP	cytochrome p-450
D/C	discontinue
dL	deciliter
DMC	Data monitoring committee
DSM IV	Diagnostic and Statistical Manual of Mental Disorders (4 th Edition)
EA	extent of absorption
ECG	electrocardiogram
eCRF	Electronic Case Report Form
EDC	Electronic Data Capture
EEG	electroencephalogram
eg	exempli gratia (for example)
ESR	Expedited Safety Report
F	bioavailability
FDA	Food and Drug Administration
FSH	follicle stimulating hormone
g	gram
GC	gas chromatography
GCP	Good Clinical Practice
GGT	gamma-glutamyl transferase
GFR	glomerular filtration rate
h	hour
HBsAg	hepatitis B surface antigen
HBV	hepatitis B virus
HCV	hepatitis C virus
HCO 3 	bicarbonate
HIV	Human Immunodeficiency Virus

Term	Definition
HR	heart rate
HRT	hormone replacement therapy
ICD	International Classification of Diseases
ICH	International Conference on Harmonisation
ie	id est (that is)
IEC	Independent Ethics Committee
IMP	investigational medicinal products
IND	Investigational New Drug Exemption
IRB	Institutional Review Board
IRT	Interactive Response Technology
IU	International Unit
IV	intravenous
K	slope of the terminal phase of the log concentration-time curve
K 3 EDTA	potassium ethylenediaminetetraacetic acid
K +	potassium
kg	kilogram
L	liter
LAM	Lactation amenorrhea method
LC	liquid chromatography
LDH	lactate dehydrogenase
ln	natural logarithm
mg	milligram
Mg ++	magnesium
min	minute
mL	milliliter
mmHg	millimeters of mercury
MR	medical research
MS	mass spectrometry
MTD	maximum tolerated dose
μg	microgram

Term	Definition
N	number of subjects or observations
Na +	sodium
N/A	not applicable
ng	nanogram
NIMP	non-investigational medicinal products
NSAID	nonsteroidal anti-inflammatory drug
PD	pharmacodynamics
PK	pharmacokinetics
PO	per os (by mouth route of administration)
QC	quality control
QD, qd	quaque die, once daily
R 	coefficient of determination
RBC	red blood cell
SAE	serious adverse event
SD	standard deviation
SOP	Standard Operating Procedures
Subj	subject
t	temperature
T	time
TAO	Trial Access Online, the BMS implementation of an EDC capability
T-HALF	Half life
TID, tid	ter in die, three times a day
Tmax, TMAX	time of maximum observed concentration
UV	ultraviolet
WBC	white blood cell
WHO	World Health Organization
WOCBP	women of childbearing potential
WNOCBP	women not of childbearing potential

## **APPENDIX 2        STUDY GOVERNANCE CONSIDERATIONS**

The term 'Participant' is used in the protocol to refer to a person who has consented to participate in the clinical research study. The term 'Subject' used in the eCRF is intended to refer to a person (Participant) who has consented to participate in the clinical research study.

### **REGULATORY AND ETHICAL CONSIDERATIONS**

#### **GOOD CLINICAL PRACTICE**

This study will be conducted in accordance with:

- Good Clinical Practice (GCP),
- as defined by the International Council on Harmonisation (ICH)
- in accordance with the ethical principles underlying European Union Directive 2001/20/EC
- United States Code of Federal Regulations, Title 21, Part 50 (21CFR50)
- applicable local requirements.

The study will be conducted in compliance with the protocol. The protocol and any amendments and the participant informed consent will receive approval/favorable opinion by Institutional Review Board/Independent Ethics Committee (IRB/IEC), and regulatory authorities according to applicable local regulations prior to initiation of the study.

All potential serious breaches must be reported to Sponsor or designee immediately. A serious breach is a breach of the conditions and principles of GCP in connection with the study or the protocol, which is likely to affect, to a significant degree, the safety or physical or mental integrity of the subjects of the study or the scientific value of the study.

Personnel involved in conducting this study will be qualified by education, training, and experience to perform their respective tasks.

This study will not use the services of study personnel where sanctions have been invoked or where there has been scientific misconduct or fraud (e.g., loss of medical licensure, debarment).

#### **INSTITUTIONAL REVIEW BOARD/INDEPENDENT ETHICS COMMITTEE**

Before study initiation, the investigator must have written and dated approval/favorable opinion from the IRB/IEC for the protocol, consent form, participant recruitment materials (eg, advertisements), and any other written information to be provided to subjects. The investigator or BMS should also provide the IRB/IEC with a copy of the Investigator Brochure or product labeling information to be provided to subjects and any updates.

The investigator, Sponsor or designee should provide the IRB/IEC with reports, updates and other information (e.g., expedited safety reports, amendments, and administrative letters) according to regulatory requirements or institution procedures.

## **COMPLIANCE WITH THE PROTOCOL AND PROTOCOL REVISIONS**

The investigator should not implement any deviation or change to the protocol without prior review and documented approval/favorable opinion of an amendment from the IRB/IEC (and if applicable, also by local health authority) except where necessary to eliminate an immediate hazard(s) to study subjects.

If a deviation or change to a protocol is implemented to eliminate an immediate hazard(s) prior to obtaining relevant approval/favorable opinion(s) the deviation or change will be submitted, as soon as possible to:

- IRB/IEC for
- Regulatory Authority(ies), if applicable by local regulations (per national requirements)

Documentation of approval/favorable opinion signed by the chairperson or designee of the IRB(s)/IEC(s) and if applicable, also by local health authority must be sent to BMS.

If an amendment substantially alters the study design or increases the potential risk to the participant: (1) the consent form must be revised and submitted to the IRB(s)/IEC(s) for review and approval/favorable opinion; (2) the revised form must be used to obtain consent from subjects currently enrolled in the study if they are affected by the amendment; and (3) the new form must be used to obtain consent from new subjects prior to enrollment.

If the revision is done via an administrative letter, investigators must inform their IRB(s)/IEC(s).

## **FINANCIAL DISCLOSURE**

Investigators and sub-Investigators will provide the Sponsor with sufficient, accurate financial information in accordance with local regulations to allow the Sponsor to submit complete and accurate financial certification or disclosure statements to the appropriate health authorities. Investigators are responsible for providing information on financial interests during the course of the study and for 1 year after completion of the study.

## **INFORMED CONSENT PROCESS**

Investigators must ensure that subjects are clearly and fully informed about the purpose, potential risks, and other critical issues regarding clinical studies in which they volunteer to participate.

In situations where consent cannot be given to subjects, their legally acceptable representatives (as per country guidelines) are clearly and fully informed about the purpose, potential risks, and other critical issues regarding clinical studies in which the participant volunteers to participate.

Sponsor or designee will provide the investigator with an appropriate (i.e., Global or Local) sample informed consent form which will include all elements required by ICH, GCP and applicable regulatory requirements. The sample informed consent form will adhere to the ethical principles that have their origin in the Declaration of Helsinki.

Investigators must:

- Provide a copy of the consent form and written information about the study in the language in which the participant is most proficient prior to clinical study participation. The language must be non-technical and easily understood.

- Allow time necessary for participant or participant's legally acceptable representative to inquire about the details of the study.
- Obtain an informed consent signed and personally dated by the participant or the participant's legally acceptable representative and by the person who conducted the informed consent discussion.
- Obtain the IRB/IEC's written approval/favorable opinion of the written informed consent form and any other information to be provided to the subjects, prior to the beginning of the study, and after any revisions are completed for new information.

If informed consent is initially given by a participant's legally acceptable representative or legal guardian, and the participant subsequently becomes capable of making and communicating his or her informed consent during the study, consent must additionally be obtained from the participant.

Revise the informed consent whenever important new information becomes available that is relevant to the participant's consent. The investigator, or a person designated by the investigator, should fully inform the participant or the participant's legally acceptable representative or legal guardian, of all pertinent aspects of the study and of any new information relevant to the participant's willingness to continue participation in the study. This communication should be documented.

The confidentiality of records that could identify subjects must be protected, respecting the privacy and confidentiality rules applicable to regulatory requirements, the subjects' signed ICF and, in the US, the subjects' signed HIPAA Authorization.

The consent form must also include a statement that BMS and regulatory authorities have direct access to participant records.

The rights, safety, and well-being of the study subjects are the most important considerations and should prevail over interests of science and society.

